## Project arrangements, method selection and analyses

### Subjects

#### Main eligibility criteria

##### Study I:

- received radical RT or RARP at SI between 01.01.2014 and 31.12.2018
- alive and living in Innlandet County
- fluent in Norwegian (orally and in writing)
- written informed consent

**Study IIa)** the subgroup of participants in Study I who were  $\geq 70$  years by the time of treatment.

**Study IIb)** a random sub-sample from Study IIb, excluding survivors with clinically significant relapse (verified metastases/local progression and/or start of lifelong antiandrogen therapy)

Clinically significant cancer relapse, occurring in approximately 10-20%, may affect all outcomes. Reliable information on this aspect cannot be retrieved before consent to participation, and as outcomes for the overall cohorts are of interest, all eligible and consenting survivors will be enrolled, and recurrence taken into account in the analyses. The exception is the subsample drawn for performance tests in Study II b (as explained above).

**Control groups:** For comparison with a general population, a control group of males matched on age and education will be drawn from the HUNT4/HUNT4 70+ surveys performed in 2017-2019, targeting all inhabitants and inhabitants  $\geq 70$  years in Trøndelag County, respectively. Jointly these surveys include broad health assessments using questionnaires, physical examinations and tests.

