**Objective 1. Statistical approach:** To investigate if global QoL (scores 1-100) (primary outcome) is associated to age at the time of treatment, we will estimate a linear regression model, allowing us to assess possibly non-linear association between global QoL and age. Since several factors may influence QoL, we will adjust the analysis for potential confounders in a multiple linear regression model. The confounders to be included are treatment modality (surgery, RT and surgery followed by RT), cancer characteristic (low/intermediate/high risk), clinical relapse (yes/no), androgen therapy (yes/no), time from treatment, social status (living alone/with partner), education (four categories), and comorbidity score. To avoid uncertainties related to any cancer relapse, we will estimate a similar regression model for patients with no biochemical and clinical relapse as sensitivity analysis. **Sample size:** For the multiple linear regression analyses, sample size according to Green's rule of thumb should at least be  $50+8*m$ , where  $m$  is the number of variables in the model. Due to categorical nature of some of the confounders, the number of variables in the model will be 13, requiring at least 154 participants. The size of the enrolled cohort of approximately 840 participants is clearly sufficient to perform the analysis with enough power.

**Objective 2. Statistical approach:** We will compare health status (a four-category primary outcome) between all older prostate cancer survivors and their matched controls by ordinal

---

 Detailed plan for analyses in separate document «statistical analysis plan»

regression model (nominal if proportional odds assumption is violated). The results will be adjusted for potential pre-defined confounder (social status, comorbidity scores, and relapse), and matching variables (age and education) to avoid residual confounding in a multiple regression model. As sensitivity analysis, the same analysis will be performed excluding survivors with clinical cancer relapse. **Sample size:** For regression model with categorical outcome to yield stable estimates, it is required at least 10 cases in the smallest outcome category per variable in the model. As the model includes 8 variables, at least 80 cases in the smallest category is required, which should be unproblematic given the expected number of older survivors (350) and thrice as many controls.

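### Objective 2 adjusts the comparison of all older survivors with controls for relapse, which only survivors can have, so no described analysis gives a confounder-adjusted effect for all survivors

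*Combined protocol and SAP*

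**What the plan says.** All references are to the combined protocol and SAP.

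- **Strategy for analyses and sample size, Objective 2.** The primary outcome, four-category self-reported health, is compared "between all older prostate cancer survivors and their matched controls" by ordinal regression. On adjustment: "The results will be adjusted for potential pre-defined confounder (social status, comorbidity scores, and relapse), and matching variables (age and education").
- **Same paragraph, sensitivity analysis.** "As sensitivity analysis, the same analysis will be performed excluding survivors with clinical cancer relapse".
- **Same paragraph, sample size.** "As the model includes 8 variables, at least 80 cases in the smallest category is required".
- **Objective 1 covariates.** Relapse is entered there as "clinical relapse (yes/no").
- **Main eligibility criteria.** Relapsed men are enrolled in the surveys: "as outcomes for the overall cohorts are of interest, all eligible and consenting survivors will be enrolled, and recurrence taken into account in the analyses". Only the Study IIb test subsample is drawn "excluding survivors with clinically significant relapse (verified metastases/local progression and/or start of lifelong antiandrogen therapy"). The same section puts clinically significant relapse at about 10–20% and says it may affect every outcome.
- **Other assessments.** Treatment for relapse is among the prostate cancer details taken from the survivors' medical records. No relapse variable is described for controls.
- **Secondary outcomes.** The confounder set of each objective is carried over to its secondary outcomes, which for Objective 2 means activities of daily living.
- **Footnote to the general statistical approach.** "Detailed plan for analyses in separate document". That document is not part of the text reviewed here.

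**The concern.** A confounder of survivor versus control must not itself result from being a survivor. Relapse does: it occurs after the cancer and its treatment, and it is part of what distinguishes the survivor group from the general population. Adjusting for it changes the question being answered.

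Two codings for controls are conceivable, and the protocol states neither. If relapse is missing in controls, a complete-case fit drops every control. If it is coded 0, which is the only workable reading, the group coefficient compares relapse-free survivors with controls, and relapsed men are described by a separate coefficient.

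The eligibility section gives two aims: to report on the overall cohort, and to take recurrence into account. The adjusted model as written serves only the second. A reader who sees the unadjusted and adjusted results side by side would put the difference down to confounding. Part of it would be the removal of relapsed men from the contrast, in the primary outcome of Objective 2 and in its secondary outcome.

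**Working it through.** **1. Is the relapse term really planned?** The stated count of 8 variables can be rebuilt, using the four education categories given under Objective 1 (3 indicator terms):

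group 1 + social status 1 + comorbidity 1 + relapse 1 + age 1 + education 3 = 8, and 8 × 10 = 80 cases.

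This matches the protocol's 80. Without relapse the count is 7, and the rule asks for 7 × 10 = 70. So relapse is a separate term in the planned model.

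**2. What the group coefficient means.** Code relapse 0 in all controls and write the linear predictor as β·group + ρ·relapse + other covariates. Controls have 0, relapse-free survivors β, and relapsed survivors β + ρ. Hence β is relapse-free survivors versus controls. Excluding relapsed men removes the cell that identifies ρ and leaves the same contrast β. An all-survivors contrast is approximately β + p·ρ, where p is the share relapsed.

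**3. Inputs.**
- From the protocol: 350 older survivors; three controls each, so 1,050; relapse 10–20%, so 350 × 0.10 = 35 to 350 × 0.20 = 70 men.
- Assumed, because the protocol gives no figure: control distribution over the four health categories 15/55/25/5%; OR for worse health in relapse-free survivors 1.2; OR for relapse 1.5 to 4.

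**4. Hand check at relapse OR 2.**
- 10% relapse: ln 1.2 + 0.10 × ln 2 = 0.182 + 0.069 = 0.252, OR 1.29.
- 20% relapse: 0.182 + 0.139 = 0.321, OR 1.38.

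**5. Large-sample proportional-odds fits.** These are maximum likelihood fits on the three cells, with standard errors (SE) from the information matrix and the other covariates omitted. The adjusted and sensitivity ORs are both 1.20 in every row.

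| Relapse OR | All-survivors OR, 10% relapse | Shift in SE | All-survivors OR, 20% relapse | Shift in SE |
|---|---|---|---|---|
| 1.5 | 1.25 | 0.35 | 1.30 | 0.69 |
| 2 | 1.29 | 0.59 | 1.38 | 1.18 |
| 3 | 1.34 | 0.93 | 1.49 | 1.86 |
| 4 | 1.38 | 1.16 | 1.58 | 2.32 |

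The SE of the log OR is 0.118 for all survivors. For the adjusted model it is 0.123 (10% relapse) and 0.129 (20%), and the sensitivity analysis has the same SEs to three decimals.

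Expected 95% confidence intervals at relapse OR 2:
- 10% relapse: adjusted 0.94–1.53, all survivors 1.02–1.62.
- 20% relapse: adjusted 0.93–1.54, all survivors 1.10–1.74.

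**6. Robustness.**
- Three other control distributions (10/60/25/5, 20/50/22/8 and 5/25/55/15%) moved no all-survivors OR by more than 0.015.
- With relapse-free OR 1.0 and relapse OR 1.5–4, the adjusted OR is 1.00 and the all-survivors OR is 1.04–1.15 (10%) or 1.09–1.32 (20%).
- A separate simulation with all planned covariates (60 replicates per scenario) gave adjusted and sensitivity group estimates that differed on average by 0.001–0.002 on the log-odds scale, for every relapse effect tried.

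**The case against.** **The planned model contains the information.** With relapse coded 0 in controls, group plus relapse is an exact reparameterisation of a three-level group variable. The all-survivors effect can be recovered as the group coefficient plus the relapse share times the relapse coefficient. At relapse OR 2 this gives 1.29 (1.02–1.62) at 10% relapse and 1.38 (1.09–1.74) at 20%, practically the same as refitting without relapse. This is correct, but the protocol describes no such step, and the coefficient that would be reported is the relapse-free one.

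**Matching already does part of the work.** The unadjusted comparison covers all survivors, against controls matched on age and education. That stands: the gap is an all-survivors effect also adjusted for social status and comorbidity.

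**The illustrations depend on chosen values.** The intervals at relapse OR 2 fall on opposite sides of 1 because the relapse-free OR was set at 1.2; at 1.0 or 1.5 no such flip occurs at that relapse OR. If relapse-free survivors were healthier than controls (say OR 0.80), the all-survivors OR at 10% relapse and relapse OR 2 would be 0.86, and the adjusted result would be the one further from 1. Shifts near 2 SE need 20% relapse and a relapse OR of 3–4, and the protocol attaches no time frame to its 10–20%. All this stands. It limits what can be said about size; it does not change which contrast the adjusted model estimates.

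**The text leaves room.** Men with prostate cancer are not expressly excluded from the controls, and the separate analysis plan may settle the coding and the main model. Both are fair reservations. Even so, no relapse data are described for controls.

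**Conclusion.** The concern holds for the analyses the protocol describes. The adjusted Objective 2 model estimates relapse-free older survivors versus controls, although the stated comparison is of all older survivors.

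Reading relapse as clinical relapse, as Objective 1 and the sensitivity analysis both do, the sensitivity analysis nearly duplicates the adjusted one whatever the effect of relapse. It is a different contrast only when set against the unadjusted comparison.

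The numerical consequence rests on assumed relapse effects. It is nil if relapse does not affect self-rated health, modest at relapse OR 1.5–2 (0.35–0.59 SE at 10% relapse, 0.69–1.18 SE at 20%), and up to 2.32 SE at relapse OR 4 with 20% relapsed. If relapse worsens health, the adjusted log OR for worse health lies below the all-survivors one. The SEs are approximate because the fits omit the other covariates. This should be fixed; confidence is medium because the separate analysis plan was not available.

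**What to change.** 1. Remove relapse from the adjusted Objective 2 model and from the models for its secondary outcome. The adjusted effect is then all older survivors versus controls, given age, education, social status and comorbidity.
2. State whether this or the unadjusted comparison is the main result.
3. Take recurrence into account through the existing analysis that excludes clinically relapsed men, which then becomes a genuinely different contrast, or through an additional model with a three-level group (control, relapse-free survivor, relapsed survivor). The three-level model also keeps the estimate for relapsed men that the planned term would have given.
4. Say clinical relapse wherever Objective 2 says only relapse.
5. Restate the model as 7 variables and at least 70 cases in the smallest category.
6. Check all of this against the separate statistical analysis plan.

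The cost is one or two lines of wording. No new data are needed, and with the three-level model no planned contrast is lost.

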### *Strategy for analyses and sample size*

**Available and expected number of participants:** About 400 men with prostate cancer received curative RT at SI from 2014 to 2018, about 250 of these were older ( $\geq 70$  years) by time of treatment. In the same period about 1000 men underwent RARP, about 1/3 (330) being older. Thus, our target population includes about 1400 men of all ages, and about 580 older men. Estimating a response rate of 60%, our overall sample will include about 840 men of all ages (about 240 and 600 men having undergone RT and RARP, respectively), and about 350 older men (about 150 and 200 receiving RT and RARP, respectively). Matched controls will be drawn from the HUNT4 and HUNT4 70+ surveys, distribution 1:3 (cancer survivors : controls).

**General statistical approach:** Simple descriptive statistics will be used to describe our cohorts. Comparison between groups will be made using parametric and non-parametric statistics as appropriate. To assess the impact of age, treatment regimen and relevant confounding factors on outcomes, multiple regression models will be estimated.

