**Objective 3. Statistical approach:** We will compare SPPB scores (primary outcome) between the older prostate cancer survivors and their matched controls by bivariate linear regression model, and adjust the results for potential pre-defined confounders (social status, comorbidity scores and health status) and matching variables (age and education) to avoid the residual confounding in a multiple linear regression model. **Sample size:** According to Greens's rule of thumb, with 10 variables in the multiple model we will need at least 130 participants to obtain valid estimates. To cover for possible registration failures for some participants, we will include a random sample of 150 from the older participant group and thrice as many matched controls for these analyses.

**Secondary outcomes** will be assessed in the same way as the primary ones for each objective. The same confounders will be included into the multiple models. The type of regression model will be considered based on the nature of each outcome analysed

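### Objective 3: the plain linear regression of SPPB on 150 survivors and 450 matched controls should use robust standard errors (cheap improvement, minor)

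*Combined protocol and SAP*

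**What the plan says.** Under *Strategy for analyses and sample size*, Objective 3, the plan states: "We will compare SPPB scores (primary outcome) between the older prostate cancer survivors and their matched controls by bivariate linear regression model". A second step is to "adjust the results for potential pre-defined confounders (social status, comorbidity scores and health status") and for "matching variables (age and education) to avoid the residual confounding in a multiple linear regression model". For numbers, "we will include a random sample of 150 from the older participant group and thrice as many matched controls for these analyses", that is, 150 survivors and 450 controls.

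The controls are described in two places. Under the eligibility criteria, "a control group of males matched on age and education will be drawn from the HUNT4/HUNT4 70+ surveys"; under the expected numbers, the ratio is given as "distribution 1:3 (cancer survivors : controls"). Neither place says whether each survivor gets his own three controls (individual matching) or whether the control group as a whole is balanced on age and education (frequency matching). The Study IIb survivors are a random sub-sample, "excluding survivors with clinically significant relapse".

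Secondary outcomes follow the approach of the primary outcome for their objective, with the type of regression chosen to suit the outcome. A footnote to the general statistical approach refers to a separate statistical analysis plan for detail.

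**The concern.** Two features of the design affect the standard error of the survivor-control difference, and the stated model does not mention either.

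- **Matching.** Members of a matched set share age and education. If these predict SPPB, the members are positively correlated, and an unadjusted regression that treats all 600 men as independent overstates the standard error.
- **Unequal variance at 1:3.** Ordinary regression pools the residual variance. With equal group sizes, unequal variances cancel in the standard error of the difference. At 150 against 450 they do not: the pooled variance is dominated by controls, while the true variance of the difference is dominated by survivors.

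The groups arise differently. Survivors were selected for radical treatment, consented, and had relapse removed; controls come from a general population survey. Equal variances therefore cannot be taken for granted. At stake are the confidence interval and p-value of a primary outcome, and of any secondary outcome analysed by the same kind of linear model. Objective 2 has a stated fallback if its proportional odds assumption fails; Objective 3 has none for equal variance.

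**Working it through.** **The plan's own figure.** Green's rule, 50 + 8 × m, with m = 10 gives 50 + 80 = 130, as stated. The 10 can be recovered as group 1, social status 1, comorbidity 1, health status 3 (four categories), age 1, education 3 (four categories). The adjusted model therefore does contain both matching variables.

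**Inputs.** From the plan: n1 = 150, n0 = 450, matched on age and education. Assumed, because the documents give none: the share of SPPB variance explained by age and education (R²), and the ratio r of survivor to control SD.

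**Step 1: matching ignored, equal variances, unadjusted model.** Ratio of stated to true standard error = 1/√(1 − R²).

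- R² = 0.10: 1/√0.90 = 1.05, type I error 3.9%
- R² = 0.20: 1/√0.80 = 1.12, type I error 2.8%

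The error is in the conservative direction.

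**Step 2: age and education in the model, equal variances.** Simulation of 3000 matched data sets per scenario (assumed: control residual SD 2.0, age slope −0.12 per year, 0.2 per education level). The ordinary standard error was 1.01 to 1.02 times the true one and the type I error 4.5% to 4.8%, including with a residual set correlation of about 0.08 or a curved age effect. With scores capped to 0-12 (assumed range) the figures were 1.005 and 5.0%. The planned adjustment largely removes the problem in step 1.

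**Step 3: unequal variances at 150 against 450.** With control SD = 1:

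- true variance = r²/150 + 1/450
- pooled variance = [(149r² + 449)/598] × (1/150 + 1/450)
- k = √(pooled/true); type I error = 2 × [1 − Φ(1.96k)]; power of an effect sized for 80% = Φ(2.80 − 1.96k)

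For r = 0.8: true = 0.00649; pooled = 0.9103 × 0.00889 = 0.00809; k = 1.12.

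For r = 1.2: true = 0.01182; pooled = 1.1096 × 0.00889 = 0.00986; k = 0.91.

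| Survivor/control SD | k | Type I error | Standard error |
|---|---|---|---|
| 0.7 | 1.19 | 2.0% | 19% too wide; 80% power becomes 68% |
| 0.8 | 1.12 | 2.9% | 12% too wide; 80% power becomes 73% |
| 1.0 | 1.00 | 5.0% | correct |
| 1.2 | 0.91 | 7.3% | 9% too narrow |
| 1.5 | 0.82 | 10.7% | 18% too narrow |

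Adjusting for age and education does not help here. In the simulation the adjusted ordinary standard error at r = 0.8 was 0.1799 against a true 0.1613 (1.115). A second simulation at the same ratio gave 0.171 against 0.158 (1.08), so about 8% to 12% is a fair reading.

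**Step 4: the remedy.** In the adjusted model, HC3 and set-clustered standard errors gave type I error between 4.3% and 6.0% in every scenario (SD ratios 0.67 to 1.5). Simulation error at 5% is about √(0.05 × 0.95/3000) = 0.4 percentage points.

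**The case against.** A reader might infer that both regressions ignore the matched sets and that the error bars of a primary outcome are therefore wrong. The documents do not support that. The multiple model includes both matching variables, and with equal variances its standard error is within about 2% of the truth. Nor does ignoring the matching create false positives: in the unadjusted model it only makes the test conservative.

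The rest depends on an assumed variance ratio. No SPPB SD is given for either group, and the ratio that matters is the residual one, after adjustment for health status, comorbidity and social status. Selection for treatment and removal of relapse, if they matter, suggest less variable survivors, which is again the conservative direction. Little in the documents points the other way. Testing of some survivors locally or at home by community staff could add variability, but this is speculation. These points stand: unequal variance is a possibility and not a finding, and no statement that the secondary outcomes are mis-sized can be made, since their model type is left open.

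Two further points stand in part. Clustering presupposes individual matching, which is not stated, so the remedy must cover both cases. Detail is deferred to a separate statistical analysis plan that is not in the text available here, so the standard error may already be specified there. However, the model that is stated is plain linear regression, and a variance estimator that does not depend on the unknown ratio is better in either direction at almost no cost.

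**Conclusion.** A cheap improvement of minor severity. The unadjusted standard error is too wide whenever age and education predict SPPB, by about 5% to 12% if R² is 0.10 to 0.20. The adjusted standard error is approximately right under equal residual variances. Because allocation is 1:3, both would be mis-sized if variances differ: 12% too wide (type I error 2.9%) at an SD ratio of 0.8, 9% too narrow (7.3%) at 1.2. R² and the SD ratios are assumptions, so the second part is an exposure that the plan leaves open and not an error that it contains.

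**What to change.** Add to the Objective 3 text, or confirm in the separate analysis plan:

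- whether matching is individual or by frequency;
- that all linear survivor-control models, unadjusted and adjusted, use heteroscedasticity-robust standard errors with a small-sample correction: clustered on matched set (for example CR2) if matching is individual, HC3 without clustering if it is by frequency;
- that the adjusted model, with age and education retained, is the primary one. This matters most under frequency matching, where HC3 alone does not remove the conservatism of the unadjusted model.

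The cost is one or two sentences and a software option; individual matching also requires the set identifier to be kept in the data. Point estimates do not change. If variances are in fact equal, the loss of precision with 150 sets is negligible.
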